The screening period consists of a screening visit (informed consent and preliminary eligibility assessment are obtained); a washout phone contact during which eligibility based on laboratory test results will be reviewed and, as needed, patients will be given instructions to washout (discontinue) oral analgesic or topical pain therapy; a washout interval (if needed) of variable/flexible length during which appropriate patients will discontinue oral analgesic therapy, topical pain therapy, and/or non-pharmacologic therapies; and a baseline pain assessment interval, when each eligible patient will be given an eDiary to record pain intensity from days -10 to -1. (To allow for training in the use of eDiaries, patients will use eDiaries from day -10, but baseline pain assessment will be defined as the last 7 days prior to randomization, ie, calculated from the values recorded from days -7 through -1). During the baseline

pain assessment interval, rescue medications for PHN pain will not be allowed. Rescue medication will also not be allowed during the last 7 days of treatment. Starting with the baseline pain assessment interval, patients will use eDiaries to record pain, using an 11-point NRS each morning (0700 \pm 2 hours) and evening (1900 \pm 2 hours), and any rescue pain medication usage. [REDACTED]

At visit 3 (day 1, randomization), visit 4 (day 15 \pm 1, week 2), and visit 5 (day 29, week 4), the NPSI and the DSIS will be administered, and the results will be recorded. On the same visit days, the results of maximal intensity evoked allodynia and maximal intensity evoked hyperalgesia will be recorded. The NePIQoL will be evaluated at visit 3 and visit 5. The PGIC will be evaluated at visits 4 and 5. Efficacy measures are not collected at visit 6 (day 57 \pm 3), except for ET visits.

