Patients will be provided with acetaminophen (TYLENOL[®], McNeil Consumer Healthcare Division of McNEIL-PPC, Inc) as 325-mg tablets in bottles of 100 tablets and allowed to take 1 to 2 tablets per dose every 6 hours, as needed, and up to 6 tablets or 1950 mg per day (over a 24-hour period) for rescue relief of PHN pain. Rescue medication will be provided at the screening visit. Rescue medication compliance will be checked at all visits until used rescue medication is collected after the baseline pain assessment interval or at randomization for patients not continuing in the study, at visit 5 (day 29, week 4) for patients who complete the treatment period or at the ET visit for patients who prematurely discontinue study drug.

No other rescue medications will be provided or allowed from the washout phone contact through visit 5 (day 29, week 4) or the ET visit. Patients will not be permitted to use rescue medication during the baseline pain assessment interval (days –10 through –1) and during the final week of treatment (the 7-day period before visit 5). During the washout interval, rescue medication use (dates of use and dose taken) will be recorded as concomitant medication. During the baseline period and the treatment period, rescue medication use will be recorded using the eDiary.

At the randomization visit (visit 3, day 1), eligible patients will be randomly assigned via IRT in a 1:1:1 fashion to 1 of 3 treatment groups: 4% w/w TV-45070 ointment, 8% w/w TV-45070 ointment, or placebo ointment.

Randomization will be stratified by test results of the pharmacogenomic sample collected at the screening visit (homozygous minor allele [positive, AA], heterozygous [positive, AG], and homozygous common allele [negative, GG]) for R1150W polymorphism in the *SCN9A* gene. The patient will be instructed on how to apply the study drug. Under study site staff supervision, the area affected by PHN pain will be carefully defined by mapping the area of pain, and dosing will be prescribed to fully cover the affected area.

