1.5.2. Justification for Use of Placebo

The use of placebo is necessary because there is no alternative method for establishing the efficacy of TV-45070 for chronic pain. Pain is a subjective condition, and there is no gold standard treatment for PHN that provides universally effective pain relief. The risk to patients for withholding alternative therapies for pain relief is negligible, and patients are free to withhold their consent for doing so and may withdraw from the study at any time. Rescue medication will be permitted once the subject has completed their baseline period.

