9.6.1.2. Sensitivity Analysis

Sensitivity analysis on the primary efficacy variable, while taking discontinuation reason and rescue medication usage into consideration, may be performed.

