### 6.2.3. Sensitivity Analysis

Two sensitivity analyses will be performed in order to assess the robustness of the results of the primary analysis to changes in the assumptions and data characteristics. The first sensitivity analysis is a multiple imputation method to handle missing weekly average of the daily average NRS pain scores for week 4. Consistent with the recommendations of the National Academy of Sciences report (National Research Council 2010), under the assumption of missing at random (MAR) and taking into account of potential bias towards the active arm for patients who withdrew from the study due to adverse events, the following steps will be carried out in SAS using the MI, Mixed, and MIANALYZE procedures:

- Step 1: prepare data set for MI procedure (PROC MI)

The following auxiliary variables are to be included in the model for PROC MI:

- Treatment (1=placebo, 2=TV45070 4%, 3=TV45070 8%)
- R1150W genotype (1=AA, 2=GA, 3=GG)
- All observed pain scores, screening, baseline, and weekly averages at each post randomization week (week 1, week 2, week 3, week 4)

The treatment will be coded to 1 (placebo) for those in the active arms withdrawn from study due to an adverse event or lack of efficacy. Thus, the missing week 4 pain scores will be imputed based on the observed placebo patient's data. In order to adjust for the use of rescue medication at week 4, the average weekly pain intensity at week 4 will be set to missing for patients who used an excessive amount of rescue medication during the week before the multiple imputation. Excessive use of rescue medication is defined as the use of rescue medication on at least 4 out of 7 days of the week 4 treatment.

- Step 2: run PROC MI. The following SAS code may be used to generate the imputed data sets:

```

Proc mi data=datain nimpute=5 seed=598719001 out=mi_out
  Maximum=10 minimum=0 round=0.01;
  Class treat genotype;
  Var treat genotype screening baseline week1 week2 week3 week4;
  Monotone reg;

```

Run;

Note: if the missing data pattern is not monotonic, a Markov Chain Monte Carlo (MCMC) method will be used instead of a regression method for imputing missing data. R1150W genotype will be used, with all 3 possible categories.

- Step 3: run mixed procedure (PROC MIXED) using the data from PROC MI

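### The SAP 6.2.3 imputation of week 4 pain omits rescue use in weeks 1 to 3, so imputed pain may be somewhat too low: a minor gap that is cheap to close

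*Protocol*

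**What the plan says.** **Rescue rules.** Protocol 1.5.2 states: "Rescue medication will be permitted once the subject has completed their baseline period". The ceiling is "up to 6 tablets or 1950 mg per day (over a 24-hour period) for rescue relief of PHN pain" (Protocol Synopsis, 3.1 and 5.4). For the final week the protocol adds: "Rescue medication will also not be allowed during the last 7 days of treatment". SAP 6.2.1 builds the week 4 average from days 22 to 28, so the ban covers the endpoint week.

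**Recording.** "During the baseline period and the treatment period, rescue medication use will be recorded using the eDiary" (Protocol Synopsis and 3.1). Protocol Table 1, footnote ee, adds that use is recorded even when it is prohibited.

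**Imputation model.** SAP 6.2.3, Step 2, lists the variables: "Var treat genotype screening baseline week1 week2 week3 week4". None of them measures rescue. Rescue enters only at week 4, where a score is set to missing for excessive use, "defined as the use of rescue medication on at least 4 out of 7 days of the week 4 treatment".

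**Who is imputed (SAP Table 2).** In Sensitivity 1, all dropouts and all completers with excessive rescue are imputed from the model. Active-arm patients who left for an adverse event or lack of efficacy are coded as placebo. In Sensitivity 2, patients in any arm who left for those two reasons receive their baseline value (BOCF), and the rest are imputed from the model.

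**Protocol 9.6.1.2** says that a sensitivity analysis, "while taking discontinuation reason and rescue medication usage into consideration, may be performed".

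**The concern.** Pain in weeks 1 to 3 is measured with rescue available; week 4 pain is measured with rescue prohibited. Take two patients in the same arm with the same genotype and the same pain history. One took no rescue in weeks 1 to 3 and the other took it daily. The model gives both the same predicted week 4 score, although the second patient's earlier scores may be low because of the acetaminophen.

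The stated assumption is missing at random given the listed variables. That is less plausible when an observed variable that may be related both to missingness and to week 4 pain is left out. For completers with excessive rescue the link to missingness needs no inference: rescue use in week 4 is the reason their score was removed. The plan judges that score unusable, then refills it from weeks 1 to 3 scores that may carry the same influence.

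At stake is how well the two sensitivity analyses specified in SAP 6.2.3 test the primary result, with about 20% dropout expected.

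**Working it through.** **1. The plan's own figure and the scale it sets.** Inputs from Protocol 9.2: difference 1.0, SD 2.35, two-sided 5%, 80% power, 20% dropout.
- Normal approximation: n = 2 × (1.960 + 0.842)² × 2.35² / 1.0² = 86.7, so 87 per arm. The t-based calculation gives 88 (power 0.802). 88 / 0.80 = 110. The plan's figures reproduce.
- Standard error of a difference at 88 per arm: 2.35 × √(2/88) = 0.354.

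**2. What has to be assumed.** The documents give no acetaminophen effect on the NRS, no frequency of rescue use and no relation between rescue and dropout. The masking by daily rescue was therefore varied from 0 to 2.0 points.

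**3. Error by hand, one scenario.** Assume 28.6% heavy users (rescue on 70% of days in weeks 1 to 3, against 10% for others), with dropout of 35% and 12%.
- Dropout: 0.286 × 0.35 + 0.714 × 0.12 = 0.186.
- Heavy share of completers: 0.286 × 0.65 / 0.814 = 0.228. Their mean rescue fraction: 0.228 × 0.7 + 0.772 × 0.1 = 0.237.
- Heavy share of dropouts: 0.286 × 0.35 / 0.186 = 0.54. Their mean rescue fraction: 0.54 × 0.7 + 0.46 × 0.1 = 0.424.
- The model is fitted to completers, so their average level of rescue is already absorbed. Only the excess can bias the prediction: 0.424 − 0.237 = 0.187 for all dropouts and 0.7 − 0.237 = 0.463 for heavy users. With 1.0 point of masking, the error is therefore at most about 0.19 and 0.46 points.

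**4. Error by simulation.** Same scenario, also run with 32.1% heavy users, and with patients followed for 1 or 3 weeks before dropout. Weekly residual SD is 2.0 and within-patient correlation 0.75. Error is imputed minus true week 4 score under the SAP variable list:

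| Masking by daily rescue | Heavy-user dropouts | All dropouts |
|---|---|---|
| 0 | −0.007 to −0.002 | −0.015 to −0.005 |
| 0.5 | −0.21 to −0.15 | −0.09 to −0.08 |
| 1.0 | −0.41 to −0.31 | −0.17 to −0.15 |
| 1.5 | −0.60 to −0.48 | −0.25 to −0.22 |
| 2.0 | −0.78 to −0.64 | −0.34 to −0.28 |

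With rescue use added as a predictor, the error is −0.004 to +0.004 for heavy users and −0.013 to −0.003 for all dropouts. That is no larger than when rescue has no effect.

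Two other sets of assumptions, in which rescue rises with pain and missingness rises with rescue, used the same 0.5 to 2.0 points of masking. They gave average errors of −0.45 to −0.05 and −0.33 to −0.03 per imputed patient. In the second, completers blanked for excessive rescue were 0.13 to 0.63 points too low. Rescue auxiliaries brought the average error to within about 0.015, and to within about 0.03 for blanked completers.

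**5. Treatment difference.**
- Same rescue pattern in every arm: a shift of at most 0.005, indistinguishable from the run with no rescue effect.
- Missingness differing between arms by 4 to 6 percentage points: simulated shift 0.003 to 0.021. Error times gap gives a similar range: 0.05 × 0.04 = 0.002 to 0.45 × 0.06 = 0.027.
- Gap of 15 points: 0.45 × 0.15 = 0.07.
- Equal 20% dropout, but the heavy-user share of dropouts differing by 10 to 30 points: 0.20 × 0.10 × 0.25 = 0.005 to 0.20 × 0.30 × 1.0 = 0.06. The 1.0 exceeds any simulated error.
- In standard errors: 0.003 / 0.354 = 0.01, 0.021 / 0.354 = 0.06, 0.07 / 0.354 = 0.20.

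**The case against.** The strongest reply is that this hardly matters. Most plausible shifts are a few hundredths of a standard error. The largest needs the worst per-patient error together with a 15-point missingness gap that nothing in the documents supports. That stands, and it is why the point is minor.

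SAP Table 2 also protects part of the group. In Sensitivity 2, adverse-event and lack-of-efficacy dropouts receive a baseline taken while rescue was prohibited, so this error cannot reach them. In Sensitivity 1, coding active-arm dropouts of this kind as placebo is a deliberate penalty, but their prediction still uses weeks 1 to 3 scores.

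A reader might infer more than the documents support:
- That heavy rescue users who drop out are imputed with too little pain, as a fact. This needs rescue to lower scores and to be commoner among those imputed; neither is documented.
- That the model uses pain scores alone, or that the plan ignores rescue. Treatment and genotype are in the model, and excessive week 4 use blanks the score.
- That week 4 is strictly free of rescue. Scores with use on 1 to 3 of 7 days are kept. The simulation in step 4 treats week 4 as rescue-free, which enlarges the contrast.
- That Protocol 9.6.1.2 requires rescue in the imputation model. It is permissive, and the SAP does use both discontinuation reason and rescue.
- That rescue drives the change from week 3 to week 4. Nothing in the documents shows this.

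Finally, the primary MMRM (SAP 6.2.2) also draws on weeks 1 to 3 with no rescue term, and the proposed fix leaves it as it is. That is true, but a sensitivity analysis is a natural place to relax the assumption.

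**Conclusion.** The omission is real and of minor importance. SAP 6.2.3 predicts a score for a week in which rescue is prohibited from weeks in which it is allowed, without the rescue record that the eDiary holds. The imputed score is too low only if rescue lowers pain ratings and patients with missing or blanked week 4 data used more of it; with no rescue effect the error vanishes.

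Under 0.5 to 2.0 points of assumed masking, the average error is about 0.03 to 0.45 points per imputed patient, and up to about 0.8 for heavy users. The treatment difference moves by about 0.003 to 0.07 points, and by almost nothing if rescue patterns match across arms. The documents do not settle the direction: more rescue-related missingness on placebo would understate the benefit, and more on active treatment would overstate it. The case for a change rests on its low cost and on a more credible missing-at-random assumption, not on any expectation that conclusions would reverse.

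**What to change.** In SAP 6.2.3, add the number of days with rescue use in each of weeks 1, 2 and 3 to the Step 1 list of auxiliary variables and to the PROC MI variable list, for both sensitivity analyses.

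- Use days (0 to 7), which fit the bounds of 0 to 10 already in the code. Tablets can reach 6 × 7 = 42 a week and would need bounds set per variable.
- Place each week's count next to that week's pain score, so that a patient who leaves after a given week still has a monotone pattern.
- State how a week with missing diary days is counted.

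Leave the analysis ANCOVA and the rescue rules unchanged.

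The cost is three variables already collected and a line or two in the SAP. The downsides are a few more values to impute for early dropouts, with counts that may be skewed, and slightly more imputation noise. Both are small with about 330 patients.

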17.5.	Administrative Letter Dated 17 December 2014.....	124

**APPENDIX A. WASHOUT PERIODS FOR COMMON MEDICATIONS TAKEN
BY PATIENTS WITH POSTHERPETIC NEURALGIA125**

LIST OF TABLES

Table 1: Study Procedures and Assessments	57
Table 2: Washout Periods for Specific Drugs.....	125

LIST OF FIGURES

Figure 1: Study Design.....	48
-----------------------------	----

LIST OF ABBREVIATIONS AND DEFINITIONS OF TERMS**Table of Abbreviations**

Abbreviation	Term
(A)	adenine
ALT	alanine aminotransferase (SGPT)
ANCOVA	analysis of covariance
AST	aspartate aminotransferase (SGOT)
AUC	area under the drug concentration by time curve
AUC _{0-24h}	area under the concentration-time curve from 0 to 24 hours
AUC _{0-inf}	area under the concentration-time curve from time 0 to infinity
average pain	the patient-reported average pain intensity over the prior 12 hours
BMI	body mass index
bpm	beats per minute
BSA	body surface area
CCI	chronic constriction injury
CDMS	clinical data management system
CFR	Code of Federal Regulations
CIOMS	Council for International Organizations of Medical Sciences
CL	clinical leader
CL/F	apparent clearance
C _{max}	maximum observed plasma drug concentration
CNS	central nervous system
CPP	clinical project physician
CRF	case report form (refers to any media used to collect study data [ie, paper or electronic])
CRO	contract research organization
CSR	clinical study report
CYP450	cytochrome P450
CYP2C19	cytochrome P450 2C19
CYP3A4	cytochrome P450 3A4
daily average NRS score	the average of the two Numeric Rating Scale scores recorded per day (the score in the morning and the score in the evening)
DDI	drug-drug interaction(s)

Abbreviation	Term
DNA	deoxyribonucleic acid
DRF	dose range-finding
DSIS	Daily Sleep Interference Scale
EDTA	ethylenediaminetetraacetic acid
ECG	electrocardiography, electrocardiogram(s)
eDiary	electronic diary
EM	erythromelalgia
ET	early termination
EU	European Union
FAS	full analysis set
FDA	Food and Drug Administration (US)
(G)	guanine
GCP	Good Clinical Practice
GD	gestation day
GGT	gamma-glutamyl transpeptidase
GLP	Good Laboratory Practice
hERG	human ether-a-go-go-related gene
IC ₅₀	50% inhibitory concentration
ICF	Informed Consent Form
ICH	International Conference on Harmonisation
IEC	International Ethics Committee
IEM	inherited or primary erythromelalgia
INR	International Normalized Ratio
IRB	Institutional Review Board
IRT	interactive response technology
ITT	intent-to-treat
iv	intravenous
LDH	lactic dehydrogenase
LOCF	last observation carried forward
LSO	local safety officer
MAD	multiple ascending dose
MedDRA	Medical Dictionary for Regulatory Activities

Abbreviation	Term
MMRM	Mixed Model Repeated Measures
MTD	maximum tolerated dose
Nav	voltage-dependent sodium channel
NePIQoL	Neuropathic Pain Impact on Quality of Life (questionnaire, score)
NNT	number-needed-to-treat
NOAEL	no-observed-adverse-effect level
non-GLP	not conducted according to Good Laboratory Practice
NPSI	Neuropathic Pain Symptom Inventory
NRS	Numeric Rating Scale
OA	osteoarthritis
OTC	over-the-counter
PGIC	Patient Global Impression of Change (scale, score)
PHN	postherpetic neuralgia
PP	per protocol
QTc	corrected QT interval
QTcF	QT interval corrected for heart rate by Fridericia's formula
RBC	red blood cell
SAD	single-ascending dose
SDV	source document verification
SOC	System Organ Class
SOP	standard operating procedure
SUSAR	suspected unexpected serious adverse reaction
ULN	upper limit of the normal range
US(A)	United States (of America)
V/F	volume of distribution
w/w	weight per weight
WBC	white blood cell
WHO Drug	World Health Organization (WHO) drug dictionary
worst pain	the patient-reported worst pain intensity over the prior 24 hours

1. BACKGROUND INFORMATION

1.1. Introduction

Postherpetic neuralgia (PHN) is a complication of herpes zoster in which pain persists for more than 3 months after resolution of the rash. (Three months is the most commonly identified duration, although definitions of duration for PHN vary from >1 months to >6 months.)

Postherpetic neuralgia affects between 10% to 15% of people who have herpes zoster and increases with age, affecting up to 70% of those infected who are more than 70 years old (Davies and Galer 2004, Dubinsky et al 2004, Kost and Straus 1996). Elderly patients tend to have more severe and longer lasting PHN.

Postherpetic neuralgia is a classical neuropathic pain condition in which damage to peripheral sensory nerves (and the dorsal horn regions of the spinal cord) is believed to generate spontaneous peripheral neural discharges that lead secondarily to hyperexcitability of dorsal horn sensory neurons and result in exaggerated central nervous system (CNS) responses to all input, a condition known as central sensitization (Kost and Straus 1996). Typically, patients with PHN have both a zone of loss of sensation and zones of altered sensation to light touch and temperature. Pain is described as deep aching or burning in quality and may be triggered by non-painful stimulus (mechanical allodynia) or temperature change (warm or cold allodynia). It may last for years, although there is a tendency for it to wane over time. In those patients whose pain is persistent and severe, PHN becomes debilitating, markedly restricting the patient's activity and quality of life.

Despite the numerous compounds available for treating PHN, 40% to 50% of PHN patients do not respond to any treatment (Rowbotham and Petersen 2001). Antiviral therapy for acute herpes zoster has been shown to speed clearing of the rash, but a recent meta-analysis showed that it does not reduce the likelihood of the development of PHN (Li et al 2009). Antivirals also have no demonstrable benefit after the rash has cleared and are of no use once PHN is established. Tricyclic antidepressants were the first analgesic agents that showed efficacy in randomized controlled trials of PHN, and, subsequently, anticonvulsant agents, strong opioids, and topical analgesics have also demonstrated efficacy.

A topical patch containing 5% lidocaine, a nonselective sodium channel blocker (LIDODERM[®], Endo Pharmaceuticals Inc), was approved by the United States (US) Food and Drug Administration (FDA) for the treatment of PHN. In 2004, a subcommittee of the American Academy of Neurology determined that there was solid Class I evidence of efficacy for the lidocaine patch in PHN (Dubinsky et al 2004). The lidocaine patch, if perhaps less effective than other approved treatments such as gabapentin and pregabalin (Dworkin et al 2003), is considered highly efficacious in PHN, although there have been no head-to-head comparisons with other agents and the number-needed-to-treat (NNT) varies from study to study (Davies and Galer 2004). The safety and tolerability of the lidocaine patch has probably contributed most to its widespread use in PHN. Safety and the reduced risk of drug-drug interactions (DDIs) with a topical formulation are particularly relevant, given the elderly age of most patients affected by PHN and their need for concomitant medications.

TV-45070 is a novel, potent, voltage-dependent sodium channel (Nav) blocker being developed for the treatment of patients with various neuropathic pain indications. Unlike lidocaine, TV-45070 has been designed to selectively block activity in the Nav1.7 channel, which is believed to be the most important sodium channel contributing to spontaneous and hyperactive discharges emanating from peripheral nociceptive neurons. Nonclinical studies have demonstrated that TV-45070 has efficacy in several classical neuropathic pain models, with comparable efficacy to gabapentin in the chronic constriction injury (CCI) model and superior efficacy to 5% lidocaine in a topical streptozotocin-induced diabetic neuropathic pain model.

TV-45070 has been studied in a 2-period crossover trial (each period lasting 3 weeks) in 62 PHN patients who received 1 or more TV-45070 doses. Although it did not meet the primary endpoint (change in mean daily pain score during the last week compared to baseline as measured by the Numeric Rating Scale [NRS]), a significantly larger percentage of patients with 50% reductions in pain were seen during the TV-45070 treatment period in the efficacy evaluable and per protocol (PP) analysis groups. The current study is designed to further evaluate the efficacy of TV-45070 in a larger, parallel-group study design.

